8.3.1. Primary Endpoint Analysis

A Pearson's chi-square test, or Fisher's exact test if the expected cell counts are <5, will be used to compare the proportion of subjects with an ongoing pregnancy (for all pregnancies identified by 6 mos after Sono HSG) between the Lipiodol UF® and saline groups. A relative risk and 95% confidence interval will be used to quantify the effect size.

8.3.2. Secondary Endpoint Analysis

A two-sample t-test will be used to compare the Lipiodol UF® to saline groups with respect to continuous outcomes, such as VAS scores, change in Ferti-QOL scores from baseline to 6 mos after Sono HSG, and anti-chlamydial antibody levels. The effect size from the two-sample t-tests will be quantified using the difference in means and 95% confidence interval. In the event the data do not meet parametric assumptions, the data will either be transformed (e.g., a logarithmic transformation) in order to satisfy parametric assumptions or a non-parametric Wilcoxon rank-sum test will be used to compare the treatment groups.

A Pearson's chi-square test, or Fisher's exact test if the expected cell counts are <5, will be used to compare the live birth proportions, as well as detectability (yes/no) for anti-chlamydial antibodies, between the Lipiodol UF® and saline groups. A relative risk and 95% confidence interval used to quantify the effect size.

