7.2.3 Baseline Assessments/Study Intervention

Case report forms documenting the history will be obtained, the Ferti-QOL (12) quality of life survey will be obtained. Serum for Anti-Chlamydial antibodies as well as Free T4 and TSH will be drawn before or after the Sono HSG depending on the patient's reason for visit, as often a baseline progesterone and hCG level are obtained prior to the Sono HSG if the patient is to go on immediately to treatment. The rationale for the Anti-Chlamydial antibodies is that we have shown they are associated with failure to conceive and pregnancy loss including ectopic pregnancies in our prospective randomized controlled trials (9). Samples drawn for anti-chlamydial antibodies will be sent to the study sponsor's laboratory for analysis. Free T4 and TSH will be collected in order to assess thyroid function. A urine pregnancy test will be performed. We will then proceed with the Sono HSG. This begins first with a routine pelvic ultrasound. Then a speculum is inserted into the vagina and then the Sono HSG catheter is inserted through the cervical canal into the uterine cavity and the balloon is inflated to maintain a seal at the cervical canal. A special device, i.e. the FemVue system, will then be used to infuse normal saline while at the same time creating bubbles to ease ultrasound visualization. The speculum is removed and the transvaginal ultrasound probe is inserted. The Sono HSG begins with infusion of normal saline via the FemVue catheter. After a patient has had an SHG with a normal cavity and at least one patent tube as determined by the performing physician, the patient will receive the study contrast or control saline which will be in an opaque glass syringe and connected to the uterine catheter via opaque tubing to allow double blinding of physician and patient. The study agent will be shaken vigorously to induce turbulence and air bubbles to ease tracking of the agent and then infused in 2 cc increments under ultrasound

visualization while the physician again visualizes the uterine cavity and patency of the fallopian tube(s). Infusion will cease with documentation of a normal cavity and tubal patency or when 10 cc have been infused. The amount of contrast infused will be recorded. After infusion the patient will be asked to assess the degree of pain she experienced by the VAS scale and both physician and patient will be asked to document a guess as to what contrast medium was used as study agent.

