7.2.6 Final Study Contact (6 months + 2 weeks)

The final study contact will take place by mail. If the patient has not become pregnant, the patient will be mailed the follow up Ferti-QOL questionnaire to fill out with a self addressed prepaid return envelope. Any pregnancies that occur up to 6 months after randomization will be followed to completion and will not receive a FertiQol questionnaire.

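### FertiQoL change is tested without adjustment for the baseline score already collected; a baseline-adjusted model is a free gain in precision, though it does not undo the restriction to non-pregnant women

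*Combined protocol and SAP*

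**What the plan says.** Section 8.3.2 states: "A two-sample t-test will be used to compare the Lipiodol UF® to saline groups with respect to continuous outcomes". FertiQoL enters that list as "change in Ferti-QOL scores from baseline to 6 mos after Sono HSG", and the effect is to be "quantified using the difference in means and 95% confidence interval". If parametric assumptions fail, the data are transformed or "a non-parametric Wilcoxon rank-sum test will be used to compare the treatment groups". None of these options uses baseline as a covariate, and neither does anything else in section 8.3.

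The baseline score exists. The schedule in 7.2 places FertiQoL at the enrollment/study visit, and 7.2.3 confirms that "the Ferti-QOL (12) quality of life survey will be obtained" there, with no restriction to a subset.

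The 6-month score is restricted. Section 7.2.6 says: "If the patient has not become pregnant, the patient will be mailed the follow up Ferti-QOL questionnaire". Pregnancies arising up to 6 months after randomization "will be followed to completion and will not receive a FertiQol questionnaire".

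**The concern.** A change score fixes the coefficient of baseline at 1. Unless baseline and 6-month scores are almost perfectly correlated, that over-corrects and carries baseline noise into the comparison. The change is also negatively correlated with baseline: with common variance s², the covariance is (r − 1)s². An arm that starts low by chance will therefore tend to show more improvement. In groups of this size, chance imbalance can matter. A model that estimates the baseline coefficient handles both problems.

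At stake is the precision of the only quality-of-life comparison in the trial. Section 1.1 names change in quality of life as a secondary objective, and sections 1.1 and 8.2 say that the pilot is to inform a larger trial. The adjusted model would also give the baseline slope and residual SD needed to size FertiQoL in that trial.

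**Working it through.** **The plan's own figures.** The documents give no SD, correlation, target difference or power for FertiQoL, so there is nothing specific to it to reproduce. The overall size can be reproduced: 50 evaluable with 10% loss (8.2) gives 50/(1 − 0.10) = 55.6, or 56, which is the 28 per arm in 8.1.

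**How many women have a 6-month score (assumption).** Apply the ongoing pregnancy rates of the earlier trial in 2.2 to 25 evaluable per arm:
- saline: 25 × (1 − 0.285) = 17.9, about 18
- Lipiodol: 25 × (1 − 0.392) = 15.2, about 15

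This is an illustration, not a bound. With 28 per arm the same rates give 20.0 and 17.0. Counting every conception, or allowing for unreturned forms, gives fewer.

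**Variances.** Assume equal variance s² at both times and equal expected baselines in the arms. Let r be the baseline to 6-month correlation and N = n1 + n2.
- Change score: 2(1 − r)s²(1/n1 + 1/n2), with N − 2 df
- Baseline-adjusted: (1 − r²)s²(1/n1 + 1/n2)(1 + 1/(N − 4)), with N − 3 df
- Ratio, adjusted to change: (1 + r)/2, times 1 + 1/(N − 4) for the extra parameter

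**Worked case, r = 0.5, 18 v 15.** 1/18 + 1/15 = 0.1222.
- Change: √(1.0 × 0.1222) × 2.040 = 0.713 SD
- Adjusted: √(0.75 × 0.1222 × (1 + 1/29)) × 2.042 = 0.629 SD

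**Across r, 18 v 15:**

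| r | Variance ratio, with cost of one parameter | Half-width, change (SD) | Half-width, adjusted (SD) | Narrower by |
|---|---|---|---|---|
| 0.3 | 0.65 × 30/29 = 0.67 | 0.844 | 0.693 | 18% |
| 0.5 | 0.75 × 30/29 = 0.78 | 0.713 | 0.629 | 12% |
| 0.7 | 0.85 × 30/29 = 0.88 | 0.552 | 0.519 | 6% |
| 0.9 | 0.95 × 30/29 = 0.98 | 0.319 | 0.317 | about 1% |

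The inverse variance ratios correspond to 49%, 29%, 14% and 2% more women. Simulated variance ratios for these group sizes (10,000 runs each) were 0.77 at r = 0.5 and 0.88 at r = 0.7, in agreement.

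**Break-even.** The adjusted interval is narrower up to r of about 0.93 with 18 v 15, 0.96 with 25 v 25 and 0.90 with 14 v 12.

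**Power.** For an assumed difference of 0.5 SD with 18 v 15, power rises from 28% to 35% at r = 0.5 and from 43% to 48% at r = 0.7.

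**What the two analyses estimate.** Let D be the expected baseline difference between arms among the women analysed, and b the baseline slope. The change score estimates the 6-month difference minus D; the adjusted model estimates it minus bD. They differ by (1 − b)D, which is zero for b below 1 only if D = 0. Randomization gives D = 0 in the full randomized set. It does not guarantee this among women selected for not having become pregnant.

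**The case against.** A t-test on change is a standard method, valid under randomization, and it answers the objective in 1.1 of documenting change in quality of life. The trial is a pilot, FertiQoL has no power calculation and is absent from the secondary endpoints in 1.3, and no decision in the documents depends on its interval. The size of the gain rests on an unstated r and is negligible when r is high. The comparison is imprecise under either analysis. All of this stands. It limits the weight of the point but does not favour the change score at any r below break-even.

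A reader might infer three stronger things that the documents do not support:
- **That the planned test is wrong.** Only efficiency is lost.
- **That both analyses necessarily estimate the same mean difference.** Section 7.2.6 conditions the comparison on not having become pregnant, an outcome that the hypothesis in 2.3 expects treatment to change. Expected baselines may therefore differ between the groups compared.
- **That 18 and 15 are maximum counts.** They borrow rates from a trial that used fluoroscopy and a water-based comparator, primarily in unexplained infertility. This trial uses ultrasound and saline in a broader population, and 8.1 has 28 per arm rather than 25.

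**Conclusion.** The point holds as a free improvement in efficiency. Adjusting for the collected baseline narrows the FertiQoL interval for any r below about 0.93 at the illustrative sizes: by about 12% at r = 0.5, 6% at r = 0.7 and almost nothing at r = 0.9. These figures assume equal variances, equal expected baselines, and 18 v 15 women with a 6-month score. The direction is secure; the size is not, because r is unknown.

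The gain should not be mistaken for a repair of the selection in 7.2.6. That is the larger limitation on the FertiQoL result, and baseline adjustment leaves it in place. Whichever model is used, the estimate describes women who had not become pregnant and returned the form, not the randomized arms as a whole.

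**What to change.** In 8.3.2, take FertiQoL out of the t-test sentence and add text along these lines:

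> The 6-month FertiQoL score will be analysed by a linear model with treatment arm and baseline FertiQoL score as covariates. The adjusted mean difference and its 95% confidence interval will be reported; mean change by arm will be descriptive. If model assumptions are not met, the scores will be transformed or a rank-based analysis that also adjusts for baseline will be used. Because only women who have not become pregnant are sent the 6-month form, the result will be presented as a comparison among non-pregnant responders, with the number contributing in each arm.

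The other continuous outcomes named in 8.3.2 (VAS score and antibody level) are measured once, so the t-test can stay for them.

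The cost is a few sentences of plan text and one degree of freedom. No new data, visits or patients are needed. Fixing the model before unblinding also avoids a later choice between two analyses.

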1.0 Objectives

1.1 Study Objectives

The primary objective is to collect the ongoing pregnancy rate among subjects in the study. The co-primary objective is observe the safety and tolerability of Lipiodol UF®. Secondary objectives will be to document the relative pain during the Sono HSG procedure and any changes in quality of life as a result of the procedure according to the contrast agent. Exploratory outcomes will be the feasibility of blinding the patient and observer to the type of contrast medium injected at the end of the Sono HSG procedure and the prevalence of Anti-Chlamydial antibodies and association with outcomes. The results from this pilot trial will guide the design of a larger multi-center clinical trial examining Lipiodol UF® as a contrast agent during Sono HSG.

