Unrecognized tubal disease remains a leading cause of infertility in the world. Many have recommended using serum tests to document a history of pelvic infection and potential tubal disease. One of the tests that is used world-wide but remains experimental are tests for anti-chlamydial antibodies. Chlamydia remains a common sexually transmitted disease and a major cause of pelvic inflammatory disease, tubal damage, and infertility. We have previously shown that anti-chlamydial antibodies (specifically anti-Chlamydial trachomatis IgG3 seropositivity) is associated with lower pregnancy rates and higher rates of ectopic pregnancy in an infertile population undergoing first line infertility treatment with oral ovarian stimulation agents combined with either timed intercourse or intrauterine insemination.(9) We are further interested in incorporating this test into the fertility testing regimen and it may also select patients who may be more likely to conceive after Sono HSG testing (i.e. by the absence of anti-chlamydial antibodies).

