7.2 Study Procedures

	Screening	Enrollment/Study Visit Time = 0	Post Procedure = 2 – 4 weeks	Final Study Contact Time = 6 mos (+2 weeks)	Pregnancy Follow up Up to 15 mos
Inclusion/Exclusion Criteria	X				
Review Informed Consent and Obtain Per Telephone	X				
Schedule Sono HSG	X				
Collect Written Informed Consent		X			
Randomize		X			
Perform Urine Pregnancy Test		X			
Perform Sono HSG with Saline and then Study Agent		X			
Administer FertiQol Questionnaire		X		X	
Assess Patient VAS score		X			
Assess echogenicity of study media		X			
Assess adequacy of blinding by patient and physician		X			
Obtain Blood for Anti-Chlamydial Antibodies		X			

	Screening	Enrollment/Study Visit Time = 0	Post Procedure = 2 – 4 weeks	Final Study Contact Time = 6 mos (+2 weeks)	Pregnancy Follow up Up to 15 mos
Obtain blood for TSH and Free T4		X	X		
Collect adverse events since test				X	
Obtain Release of Pregnancy Records as necessary					X
Collect all pregnancy outcomes					X

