7.2.4 Post-Procedure Visit (2-4 weeks)

Participants will have a blood draw completed 2-4 weeks after the Sono HSG procedure to re-test TSH and Free T4.

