8.3 Statistical methods

The analysis dataset will follow a modified intention to treat (mITT) where all evaluable subjects will be analyzed. For the pilot study, an evaluable subject is a subject that has been randomized and has completed the Sono HSG.

Descriptive statistics for continuous data will be reported as the mean (standard deviation) or as the median (25th percentile, 75th percentile) if the distribution is not normally distributed. Descriptive statistics for categorical will be reported as a frequency and percentage. All hypothesis tests will be two-sided and tested at a significance level of 0.05. All analyses will be conducted using SAS software, version 9.4 (SAS Institute Inc., Cary, NC) or R software, version 3.3.3 (R Foundation for Statistical Computing, Vienna, Austria).

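### Section 8.3.2 tests a single procedure-visit anti-chlamydial antibody measurement between arms as an outcome, while the association of antibodies with outcomes, a stated aim, has no analysis

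*Combined protocol and SAP*

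**What the plan says.** **Purpose.** Section 1.1 lists among the exploratory outcomes "the prevalence of Anti-Chlamydial antibodies and association with outcomes". Section 2.1 says of the antibody test that "it may also select patients who may be more likely to conceive after Sono HSG testing". Section 7.2.3 justifies the draw because "we have shown they are associated with failure to conceive and pregnancy loss including ectopic pregnancies". All three treat the antibody as a predictor.

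**Timing.** In the section 7.2 schedule the row "Obtain Blood for Anti-Chlamydial Antibodies" is marked once, at the Time 0 visit. Section 7.2.3 allows the sample to be taken before or after the Sono HSG at that visit. The later draw in section 7.2.4 does not include antibodies: "Participants will have a blood draw completed 2-4 weeks after the Sono HSG procedure to re-test TSH and Free T4".

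**Analysis.** Section 8.3.2 places antibody level among the continuous outcomes compared between arms, next to VAS pain and change in Ferti-QOL: "and anti-chlamydial antibody levels. The effect size from the two-sample t-tests will be quantified using the difference in means and 95% confidence interval". It also compares "detectability (yes/no) for anti-chlamydial antibodies, between the Lipiodol UF® and saline groups", with a relative risk and 95% CI. Section 8.3 gives a general descriptive rule that covers prevalence: "Descriptive statistics for categorical will be reported as a frequency and percentage".

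**The concern.** The plan analyses the antibody in the wrong direction. Its use, as the protocol describes it, is to ask whether seropositive women conceive less often. Section 8.3.2 asks instead whether the contrast agent changes antibody level or detectability. Nothing in the documents suggests that it could, and the sampling time all but rules it out.

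Followed as written, the plan yields a p-value and a so-called effect size for serostatus by contrast agent, which say nothing about the agent. The question for which the blood is drawn is left to an analysis chosen after the data are seen, with the outcome, the definition of seropositivity and the estimator all open. The results are meant to guide a larger multi-center trial, so it is worth settling these choices beforehand.

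**Working it through.** **1. What the sampling schedule allows**

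| Item | Section | Content |
|---|---|---|
| Antibody draw | 7.2, 7.2.3 | Once, at Time 0, before or after the procedure |
| Repeat draw at 2–4 weeks | 7.2.4 | TSH and Free T4 only |
| Antibody level by arm | 8.3.2 | t-test, difference in means, 95% CI |
| Antibody detectability by arm | 8.3.2 | Chi-square or Fisher, relative risk, 95% CI |
| Prevalence | 8.3 | Frequency and percentage, no CI stated |
| Outcome by antibody status | 8.3, 8.3.1, 8.3.2, 10.7 | None |

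For blood drawn before the infusion, the agent cannot affect the result. For blood drawn after it at the same visit, an effect on a marker of past infection is implausible. Randomisation therefore makes the between-arm null true, or very nearly so. The exception is imbalance created by dropping randomised women who are not evaluable (sections 8.2 and 8.3).

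**2. The plan's own figure**

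No figure is stated for the antibody analyses. The evaluable number is 50, or 25 per group (section 8.2). Allowing for the stated 10% loss, 50 / 0.90 = 55.6, rounded up to 56, which matches section 8.1 (28 per arm).

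**3. What the planned detectability test returns when there is no difference**

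The documents give no seroprevalence, so a range is assumed. The rule was enumerated exactly over all possible tables, with equal prevalence in both arms: Pearson chi-square without continuity correction, Fisher if any expected count is below 5, two-sided 0.05.

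| Assumed seroprevalence | Rejection, 25 per arm | Rejection, 28 per arm |
|---|---|---|
| 5% | 0.1% | 0.1% |
| 10% | 1.0% | 1.0% |
| 20% | 4.4% | 3.8% |
| 30% | 5.3% | 5.2% |
| 40% | 6.0% | 4.8% |

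Under this null, every rejection is chance.

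**4. What the missing analysis could deliver**

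Inputs:
- 50 women.
- Overall ongoing pregnancy (39.2% + 28.5%) / 2 = 33.85%, from the Dutch trial rates in section 2.2.
- An assumed true relative risk of 0.5, seropositive versus seronegative.

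With seroprevalence q, the seronegative rate is p₀ = 0.3385 / (1 − 0.5q) and the seropositive rate is p₁ = 0.5p₀. The standard error is SE = √[(1 − p₁)/(n₁p₁) + (1 − p₀)/(n₀p₀)], and the 95% CI is 0.5 × exp(±1.96 SE).

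Worked case, q = 20%:
- p₀ = 0.3385 / 0.9 = 0.376 and p₁ = 0.188, with n₁ = 10 and n₀ = 40.
- SE = √(0.4318 + 0.0415) = 0.688.
- CI = 0.5 × exp(±1.348), or 0.13 to 1.93.

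| q | Seropositive / seronegative women | Expected 95% CI | Power of the chi-square/Fisher rule |
|---|---|---|---|
| 10% | 5 / 45 | 0.07–3.42 | 0.2% |
| 20% | 10 / 40 | 0.13–1.93 | 14.0% |
| 30% | 15 / 35 | 0.17–1.49 | 25.7% |
| 40% | 20 / 30 | 0.19–1.28 | 33.3% |

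If 33.85% is taken as the rate in seronegative women instead of overall, power is 0.2%, 11.6%, 18.4% and 23.7%, and the CIs run from 0.07–3.64 (q = 10%) to 0.17–1.49 (q = 40%).

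**5. Zero counts**

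At q = 20%, the chance that none of 5 seropositive women in one arm has an ongoing pregnancy is (1 − 0.188)⁵ = 35%. For all 10 it is (1 − 0.188)¹⁰ = 12.5%. An analysis by arm may therefore fail, and a fallback is needed.

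**6. Precision of prevalence**

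Exact (Clopper–Pearson) 95% CIs are 3.3–21.8% for 5/50, 10.0–33.7% for 10/50 and 26.4–54.8% for 20/50.

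**The case against.** - **The aim is exploratory and the trial is a pilot.** Such associations are often left to later description, and prevalence is already covered by the general descriptive rule. This stands as a reason to rate the point minor. It does not explain why the plan specifies the uninformative contrast and omits the informative one.
- **The by-arm comparison could be read as a check of baseline balance.** Showing serostatus by arm is legitimate, and a careful reader would know the blood was taken at Time 0. But section 8.3.2 sits under secondary endpoints, calls the levels outcomes and attaches an effect size. The fault is the tests and the framing; the tabulation by arm can stay.
- **A rejection need not be pure chance.** Section 8.2 mentions loss of evaluable women through problems with the glass syringe, which could in principle differ by arm. This is correct. The rejection rates above assume equal prevalence among evaluable women, and imbalance from exclusions is the one other explanation. Neither is an effect of the agent.
- **The size of the problem rests on assumptions.** Rejection near 5% is simply the size of the test and does not measure harm. Seroprevalence and the relative risk of 0.5 are not in the documents, and power depends on where 33.85% is anchored. All of this is fair. Both anchorings lead to the same conclusion, that the association can be estimated but not usefully tested, and the defect itself does not depend on these figures.
- **The rationale also names pregnancy loss and ectopic pregnancy.** Adding them would be a reasonable extension, since section 7.2.5 follows all conceptions to completion.

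**Conclusion.** The concern holds, as a minor one. The two between-arm antibody tests cannot inform on the contrast agent, and the association promised in section 1.1 has no planned analysis. The textual finding needs no assumption beyond the implausibility of a same-visit effect on a marker of past infection.

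The size rests on assumed seroprevalence, an assumed relative risk of 0.5 and the section 2.2 pregnancy rates. On those, power does not exceed about one third, and the expected 95% CI includes 1 in every case examined. The association should therefore be estimated and not tested. The primary, safety and sample-size plans are unaffected.

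**What to change.** In section 8.3.2:

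1. Remove the between-arm tests of antibody level and detectability. Show both by arm, descriptively, with the baseline characteristics. Because the draw may fall either side of the infusion, it would help to note which applies.
2. Report overall prevalence of detectable antibodies in the mITT set with an exact 95% CI.
3. Add, labelled exploratory and without a hypothesis test, the relative risk of ongoing pregnancy and of live birth in seropositive versus seronegative women, with 95% CI. Stratify by or adjust for arm where cell counts allow, and otherwise leave it unstratified. The wording should state the count below which stratification is dropped.
4. If no seropositive woman conceives, report the counts and the exact CI of each proportion.
5. Optionally, tabulate pregnancy loss and ectopic pregnancy by serostatus.

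The cost is SAP wording only, with no new data or visits. The drawback is that the estimate will be imprecise at about 50 women and can serve only to inform the larger trial.
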